### 7.3 Missing data plan

The number of missing samples will be minimized, but some samples will be missed due to clinical care logistics. A complete case analysis will be the primary analysis. An imputation based analysis will be a secondary analysis. Specifically, the last observation carried forward (LOCF) and multiple imputation method based on the Markov Chain Monte Carlo technique will be utilized to perform the imputation based analyses. A sensitivity analysis will be conducted to compare the results of the complete case analysis with the results of the imputation based analysis.

### 7.4 Interim analysis plan

At each completion of 25 subjects, an interim analysis will be done to ensure subject safety and to assess preliminary positive and negative predictive value of the BDV infection indicator. If at least one subject did not develop an infection during the study period, then additional enrollment will be stopped, and inclusion criteria will be reviewed. Subject safety will be assessed. If any significant risks to subject safety are identified, then additional enrollment will be stopped, and safety considerations will be assessed.

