#### 3.1.2 Exclusion criteria

- 1) known or suspected infection at time of enrollment
- 2) known use of systemic antibiotic, antimicrobial and/or antifungal therapy within the seven (7) days prior to hospital admission
- 3) currently active cancer, defined as receiving treatment or intend to receive treatment within hospital stay for cancer (including but not limited to: radiation, chemotherapy, systemic orals, etc)
- 4) if not intubated, unable to cooperate with providing a breath sample

- 5) expected death within 24 hours of enrollment or lack of commitment to aggressive treatment by family/medical team (e.g., likely to withdraw life support measures within 24 hrs of screening)
- 6) female who is pregnant or lactating (negative serum or urine pregnancy test results within 48 hours of enrollment or to be performed during screening)
- 7) prisoner
- 8) known participation in an investigational and interventional research study within 30 days prior to enrollment, not approved in advance by sponsor (note: to be eligible, any interventional treatment must have ended at least 30 days ago)
- 9) Individuals who are directly affiliated with sponsor or study staff, or their immediate families. Immediate family is defined as spouse, domestic partner, parent, child, or sibling whether legally adopted or biological.
- 10) Any patient that is deemed unfit for study participation, per the Investigator's discretion.

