## **7.0 Data analysis and statistical considerations**

### **7.1 Sample size determination**

For trauma patients admitted to an ICU, the mean overall nosocomial infection rate is 6 to 18%. (9, 19, 20) The incidence rate of infection could be greater for all surgical ICU patients. Data collected to date indicate that a sustained decrease in BDV of 2.0‰ or more correlates with the onset of infection when the subject is used as his-her control. The average intra subject standard deviation (SD) across time points in 32 mechanically ventilated subjects previously studied was 1.16‰, regardless of the underlying medical conditions. The inter subject SD is expected to be 1.5‰ at most. Using the BDV measurements during the breath sample monitoring period (breath sample assessments every 4 hours), the expected overall SD of the mean BDV measurements (across time points) is less than 1.5‰.

Furthermore, during the monitoring period, the mean difference in the BDV between subjects who are diagnosed with a nosocomial infection and subjects not diagnosed with an infection is expected to be 2.0‰ or more (primary hypothesis). This difference will be considered to be the minimum difference with clinical importance.

Assuming that 5% of the subjects will have a confirmed nosocomial infection over the monitoring period and an overall standard deviation of 1.5‰, a total sample size of 100 subjects (5 infected and 95 non-infected) is required to detect a minimum clinically-important difference of 2.0‰ with at least 80% power at the two-sided 5% significance level.

If the actual rate of nosocomial infections is 10%, then the proposed total sample size of 100 subjects will provide 98% power to detect a mean difference of 2.0‰. Assuming SD to be 1.5‰ (at most) for the change in BDV before and after the diagnosis of an infection is made, a total sample size of 100 subjects and an infection rate of 5%, a mean decrease of 2.0‰ prior to and after the confirmed infection will be detected with 79% power at the one sided 5% significance level (secondary hypothesis).

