If the rate of nosocomial infections is 10%, then the mean decrease of 2.0‰ will be detected with 99% power. The proposed sample size of 100 subjects is sufficient to provide accuracy in estimating the specificity of the BDV analyzer. That is, with a sample size of 100 and assuming that 95% of the subjects will have no confirmed nosocomial infection, the specificity will be estimated with a standard error of less than 5%, and the 95% confidence interval of the estimated specificity will be no greater than 20%.

To account for a missing value rate -- due to study withdrawal (see 5.12 Withdrawal of subjects) or infection failure of up to 10%, the total enrollment target is 110.

***The goal sample size of 100 subjects will be achieved through implementation of the protocol at more than one approved study site.***

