### Interim analysis plan

After completion of 25 subjects, an interim analysis will be done to ensure subject safety and to assess positive predictive value of the BDV for progression to severe sepsis and septic shock. If no subject progressing to sepsis or septic shock subjects had a positive BDV test, then additional enrollment will be stopped, and inclusion criteria will be reviewed. The study will not be stopped for superiority.

Subject safety will be assessed. If any significant risks to subject safety are identified, then additional enrollment will be stopped, and safety considerations will be assessed. During interim data analysis subgroups will be reviewed. Particular subgroups will be targeted for enrollment as necessary.

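### Protocol 7.4 stops further enrolment on the outcome planned for 95 of 100 subjects, and the SAP's different interim rule does not repair it

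*Protocol*

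**What the plan says.** Protocol 7.4 sets repeated looks: "At each completion of 25 subjects, an interim analysis will be done". They cover safety and the preliminary predictive values of BDV. The enrolment rule is: "If at least one subject did not develop an infection during the study period, then additional enrollment will be stopped". A review of the inclusion criteria follows. A separate safety stop in the same section is not at issue here.

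The rest of the Protocol fixes what outcome to expect. Section 3.1.2 excludes patients with "known or suspected infection at time of enrollment". Section 7.1 assumes 5% infection and states that "a total sample size of 100 subjects (5 infected and 95 non-infected) is required". It also considers 10% and cites a background range of 6 to 18%. After an allowance for losses, "the total enrollment target is 110", whereas section 3.0 speaks of up to 100 subjects.

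The SAP's interim plan (within its section 8) opens: "After completion of 25 subjects, an interim analysis will be done". One stated aim is "to assess positive predictive value of the BDV for progression to severe sepsis and septic shock". Its trigger is: "If no subject progressing to sepsis or septic shock subjects had a positive BDV test, then additional enrollment will be stopped". SAP section 5 repeats the 6 to 18% range but bases its sample size on a 50% infection rate.

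**The concern.** A stopping rule should separate a study that is going wrong from one that is going to plan. The Protocol's rule responds to a single uninfected subject, and uninfected subjects are what the trial enrols and expects. If it is followed as written, further enrolment stops at the first look whether or not anything is amiss, and section 7.4 gives no criterion for resuming.

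The SAP is where a correction would be expected, but it holds another rule. That rule concerns BDV positivity among subjects who progress, not the number of infections. It reads as one look rather than one per 25 subjects. The event also shifts, from severe sepsis and septic shock in the aim to sepsis or septic shock in the trigger. Nor does it say what happens if nobody has progressed, in which case its condition is met trivially. Readers of the two documents would therefore hold two different enrolment rules, with nothing to say which governs.

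**Working it through.** **Inputs.** Infection rates: 5% and 10% (Protocol 7.1), 6 to 18% (both documents), 50% (SAP section 5). Looks: each 25 completed subjects (Protocol 7.4). Subjects are treated as independent with a common infection rate p.

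**The plan's own figures.** Section 7.4 states no operating characteristic. The nearest stated figures are the powers behind the planned split (difference 2.0‰, SD 1.5‰, two-sided 5%), by normal approximation:
- 5/95: 2.0 / (1.5 × √(1/5 + 1/95)) = 2.906, and Φ(2.906 − 1.960) = 82.8%. Stated: at least 80%.
- 10/90: 2.0 / (1.5 × √(1/10 + 1/90)) = 4.0, and Φ(4.0 − 1.960) = 97.9%. Stated: 98%.

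Both reproduce, so the plan really does rest on a large uninfected majority.

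**Protocol rule at the first look.** Enrolment continues only if all 25 subjects became infected, so P(fires) = 1 − p^25.

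| p | p^25 (enrolment continues) | Expected uninfected, 25(1 − p) |
|---|---|---|
| 5% | 3.0 × 10⁻³³ | 23.75 |
| 10% | 1 × 10⁻²⁵ | 22.5 |
| 18% | 2.4 × 10⁻¹⁹ | 20.5 |
| 50% | 3.0 × 10⁻⁸ | 12.5 |

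The rule fires with probability of at least 0.99999997 throughout. If counts are cumulative, one uninfected subject also satisfies it at every later look.

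**If the negation is reversed** (stop when no subject has developed an infection), P(fires at 25) = (1 − p)^25: 0.95^25 = 27.7% and 0.90^25 = 7.2%.
- Cumulative counts: zero infections at a later look implies zero at 25, so the chance of firing at any look stays at 27.7% (5%) and 7.2% (10%).
- Each batch of 25 judged alone, looks at 25, 50 and 75: 1 − (1 − 0.277)³ = 62.3% and 1 − (1 − 0.072)³ = 20.0%.
- The same with a fourth look at 100: 1 − (1 − 0.277)⁴ = 72.7% and 1 − (1 − 0.072)⁴ = 25.8%. This look matters only if enrolment is still open, which depends on whether the ceiling is 100 (section 3.0) or 110 (section 7.1).

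**SAP rule when nobody has progressed.** The SAP gives no rate of progression. If progressors are a subset of the infected, the chance of zero infections in 25 is a lower bound on the chance of zero progressors: 0.94^25 = 21% at 6%, 0.82^25 = 0.7% at 18%, and 0.5^25 = 3 × 10⁻⁸ at 50%.

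**The case against.** The strongest reply is that this is a slip anyone would read correctly. Reviewing the inclusion criteria makes sense when too few infections occur, so the intended condition was presumably that no subject had been infected. That is the likeliest explanation, and it makes this a wording error rather than a considered design choice. It does not settle the rule. The documents do not confirm the intent, the SAP's trigger points to a different purpose, and Protocol 11.8 commits sites to the approved text, so they cannot quietly apply a presumed correction.

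The second reply is that the harm is limited, and this stands. A reader might infer that the trial would end with 25 subjects and about 25 × 0.05 = 1.25 expected infections, too few for the infected versus uninfected comparison. The documents do not support that. The rule stops additional enrolment once 25 subjects have completed. With sampling for up to 28 days plus follow-up, at 8–10 centres, more than 25 may be enrolled by then, and nothing in 7.4 ends their participation. Protocol 9.4 and 10.0 let the investigator, medical monitor and sponsor continue, modify or terminate the study.

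Two further inferences should be resisted. SAP section 10, which reports no deviation, may be a placeholder about the SAP's own plan; it is not good evidence that the SAP claims to match the Protocol. And 3 × 10⁻⁸ is not the chance of zero progressors under the SAP's sizing assumption, because the 50% is an infection rate.

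**Conclusion.** The Protocol rule is wrong as written and needs correction. It fires with near certainty, though not logical certainty, at every infection rate used for planning in either document. That conclusion is insensitive to the choice of rate; the figures assume independent subjects. The SAP does not repair it, since trigger, event and apparent number of looks all differ and the zero-progressor case is left open.

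The consequence is a pause in enrolment triggered by the planned outcome, together with two conflicting rules. Loss of the trial, or of its main comparisons, would require that enrolment never resume, and nothing in the documents makes that likely. A reversed negation remains a probable explanation, not an established one.

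**What to change.** Replace the enrolment-stopping sentences in Protocol 7.4 and the SAP's interim plan with one identical rule that states the event, the looks and whether counts are cumulative. The sponsor must say which purpose is meant.

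- **Too few infections.** Change the Protocol condition to: if no subject has developed an infection. Use cumulative counts, and state the chance of firing at any look: 27.7% at 5% infection and 7.2% at 10%. The counting basis must be explicit because judging batches separately raises these figures to 62.3% and 20.0% over three looks. State also whether a look at 100 can still stop enrolment.
- **A non-performing BDV.** Use the SAP trigger in both documents with one event name, and state that it does not apply when no event has occurred.

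The cost is a short text amendment to both documents, with the written IRB approval that Protocol 11.8 requires for its own changes. No new data or visits are needed. The two documents also differ on matters such as what counts as a positive BDV; the correction of the Protocol sentence need not wait for those.

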## 8.0 Risks and benefits of study participation

### 8.1 Potential risks

This study involves minimal risk to individual subjects. Other than the minor risks related to blood sample acquisition and confidentiality of protected health information, there are no significant risks of participation in this study.

#### ***Risks associated with breath sample collection***

The isotopic gas analyzer system used in this study, the Isomark Canary, is an investigational medical diagnostic device, exempt from IDE requirements in accordance with 21 CFR as described in Section 13 of this protocol. There will be no increased risk of infection, since for mechanically ventilated subjects gas sampling will be only on the expiratory mechanical ventilator circuit tubing and there will be no break in the ventilator circuit and for non-ventilated subjects gas sampling will be performed by inflating a single-use sample bag. The intervention has no impact on respiratory physiology measurements, because the gas sampling and the analysis are performed in vitro.

#### ***Risks associated with blood sample acquisition***

Blood may be collected via existing IV or arterial catheter. No IV or arterial catheters will be placed for study purposes. Risk of collecting blood samples can include infection or mild anemia. There is theoretical risk of an embolus resulting from the collection of blood from an arterial catheter, but such occurrences are rare in routine clinical practice.

#### ***Risks associated with loss of confidentiality***

There is a risk that information recorded about patients who agree to participate as study subjects will be shared with people who would not normally have access to this information.

### **Unknown risks**

This study may involve risks to the subject that are presently unforeseeable. Subjects or their LARs will be informed as soon as possible if any information is discovered that may affect the subject's health, welfare, or decision to be in this study.

## **8.2 Mitigation of potential risks**

### ***Mitigation of risks associated with blood draw***

To minimize the risk from blood draws, blood samples will be collected by trained clinical care or study team members. Subjects with low hemoglobin levels will not be required to collect study samples until hemoglobin concentration has increased to greater than or equal to 6.0 g/dL.

### ***Mitigation of risks associated with loss of confidentiality***

The confidentiality of study subjects will be protected by using coded subject information and password protected electronic files and by storing study data in locked rooms. Access to electronic files will be limited to the study team. The study sponsor, Isomark, will have access to subject data that is de-identified. Access to identifiable data will be limited to study team members of the study hospital. Any paper records will be maintained in locked rooms, and access to these records will be limited to the study team members.

## **8.3 Potential benefits**

### ***Potential benefit to an individual subject***

There is no direct benefit to the subject.

### ***Potential benefit to society***

The potential benefits of the research include earlier diagnosis of infections. If this indicator accurately discriminates infection in subjects with SIRS secondary to critical illness, it will be extremely valuable in the diagnosis and follow up of every seriously ill patient.

## **8.4 Risk vs benefit**

There is minimal risk to participating subjects. Participation in this study will not affect subjects' clinical care. There is no anticipated direct benefit to subjects, but potential benefit is that future patients may be afforded a new, more timely and accurate method of detecting onset of serious infection as a result of this study.

## **9.0 Adverse events and unanticipated problems**

### **9.1 Definitions**

Definitions are guided by the International Conference on Harmonization and the United States Code of Federal Regulations [21 CFR § 312.32].

### ***Adverse event (AE)***

An adverse event (AE) is any untoward medical occurrence in a patient or study subject who is administered a pharmaceutical product or medical device that does not necessarily have a causal relationship to this treatment or device. An AE could be any unfavorable and unintended sign (including abnormal laboratory findings), symptom, or disease temporally associated with the use of an investigational medical product, whether or not considered related to the investigational medical product. This definition includes illnesses or injuries, and exacerbations of pre-existing conditions.

### ***Serious adverse event (SAE)***

A serious adverse event (SAE) is any untoward medical occurrence that:

- results in death
- is life threatening (i.e. the subject was, in the opinion of the investigator, at immediate risk of death from the event as it occurred)
- requires or prolongs hospitalization
- results in persistent or significant disability or incapacity (i.e. the event causes a substantial disruption of a person's ability to conduct normal life functions)
- causes a congenital anomaly or birth defect, or
- is an important and significant medical event (e.g. allergic bronchospasm requiring intensive treatment in an emergency room or at home, blood dyscrasias or convulsions that do not result in in-patient hospitalization, or development of drug dependency or drug abuse) that, based upon appropriate medical judgment, may jeopardize the subject or may require medical or surgical intervention to prevent one of the other outcomes defining SAE.

### ***Unanticipated adverse device event (UADE)***

An unanticipated adverse device event (UADE) is any serious adverse effect on health or safety, any life threatening problem or death caused by or associated with a medical device, if that effect, problem or death was not previously identified in nature, severity or degree of incidence in the investigational plan or application (including a supplementary plan or application), or any other unanticipated serious problem associated with a device that relates to the rights, safety or welfare of clinical trial subjects.

## **9.2 Severity assessment**

The PI for the study site and study's independent medical monitors will determine the severity of each AE using the following terms and definitions:

**Mild:** An AE that was transient and required no special treatment, and did not interfere with usual or normal activities

**Moderate:** An AE that interfered with usual or normal activities but was ameliorated by therapeutic measures

**Severe:** An AE that was intense or debilitating, and which interfered with usual or normal activities. Recovery was aided by therapeutic measures. Discontinuation of investigational medical product administration or use might have been required.

**Life threatening:** An AE that may result in immediate risk of death from the event as it occurred and requires immediate intervention to prevent the outcome of death (This AE will be recorded as a SAE).

**Death:** An AE that results in death of the subject (This AE will be recorded as a SAE).

ICU subjects are expected to have SAEs related to their medical condition. Those expected SAEs associated with the underlying disease are to be reported in an expedited manner if the PI or co-investigator of the study site is unable to rule out the involvement of the Canary. SAEs listed below are expected and will be recorded in the study record, but will not be reported in an expedited manner to Isomark:

urinary tract infection; acute kidney injury; acute renal failure; acute lung injury; adult respiratory distress syndrome; hypotension; metabolic acidosis; hypothermia; coagulation dysfunction; decreased platelet count; diffuse intravascular coagulation; thromboembolic event (pulmonary embolus; deep vein thrombosis; cerebral infarction); fat embolism; myocardial infarction; decreased cardiac output with cardiac arrest; hepatic injury; severe sepsis or septic shock; bacteremia; pleural effusion; abdominal compartment syndrome; repeated surgeries; amputation; cardiorespiratory insufficiency

This clinical trial involves ICU patients with comorbidities, surgical, procedural and pharmacologic interventions or severe injuries. The expected mortality rate is approximately 35%. Death of a patient who is a study subject due to his or her injuries or other known medical conditions is not unexpected. Death is not an efficacy endpoint of the study protocol.

### 9.3 Causality assessment

A study independent medical monitor and study PI will determine the relationship of AEs to this study protocol using the following scale:

- Definite = AE is clearly related to the study procedures
- Probable = AE is likely related to the study procedures
- Possible = AE is possibly related to the study procedures
- Unlikely = AE is doubtfully related to the study procedures
- Unrelated = AE is clearly not related to the study procedures

### 9.4 Procedures for recording and reporting AEs, SAEs

#### ***AEs to be recorded in the study record***

AEs that occur after informed consent is obtained and which are determined to be definitely, probably, or possibly related to study procedures through the end of study participation will be recorded. All SAEs will be recorded.

#### ***Reporting timeframes***

Each AE will be assessed to determine if it meets the criteria for an SAE. If an SAE occurs, expedited reporting will follow IRB policies.

All deaths and other SAEs must be reported by the study site within 24 hours of becoming aware of the event to Isomark, with the exception of SAEs that are specifically attributed to underlying disease.

